3. STUDY DESIGN

3.1 DESCRIPTION OF THE STUDY

This is an open-label, phase I/II trial, which will assess the safety, tolerability and efficacy of a treat and extend management protocol for DME. Eyes which meet screening criteria will be enrolled into one of three treatment groups: (1) monthly intravitreal injections of 0.3 mg ranibizumab (Monthly Cohort, 30 eyes); (2) monthly intravitreal injections of 0.3 mg ranibizumab for 4 visits, followed by a “Treat and Extend” protocol based on pre-specified criteria of disease activity (T-REX cohort, 60 eyes); (3) monthly intravitreal injections of 0.3 mg ranibizumab for 4 visits combined with adjunctive Guided focal Laser photocoagulation to microaneurysms at week 4 and then every 3 months if leakage is present on fluorescein angiography, followed by a treat and extend protocol based on pre-specified criteria of disease activity (GILA cohort, 60 eyes).

Randomization Scheme:

All eyes which satisfy all inclusion/exclusion criteria will be randomized 1:2:2 into the Monthly:TREX:GILA Cohorts.

3 Treatment arms:

1. Monthly Cohort (30 eyes): Monthly intravitreal injections of 0.3 mg ranibizumab for 36 months, unless they meet pre-specified criteria for PRN treatment (indicated below). Treatment will begin at Day 0 and

subsequent study visits should be scheduled to occur every 28 (± 7) days relative to the date of the first injection. Dosing should not occur earlier than 21 days after previous treatments.

Starting at week 104, study eyes will have the opportunity to undergo treatment on a pro re nata (PRN) basis. Thus, eyes who have a central subfield thickness (CST) ≤ 325 microns at the week 104 visit, will not be given treatment at week 104. Eyes will continue to be seen every 4 weeks and will be given an intravitreal injection of ranibizumab 0.3 mg only if the CST is > 325 microns. Eyes will also receive treatment if there is a > 5 letter loss due to DME (compared to the vision at week 104), regardless of thickness on OCT.

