Study eyes which have not met criteria allowing them to extend to greater than or equal to 6 weeks for two consecutive visits by the week 52 (hard endpoint) visit will receive a series of three intravitreal injections of ranibizumab 0.3 mg every 4 weeks regardless of SD-OCT measurement. This series of three injections every 4 weeks will begin at the first treatment visit that occurs after the 52 week hard endpoint visit. The study eye will resume treatment interval determinations based on the pre-specified criteria at the time of the third monthly intravitreal injection.

The interval between study injections will not exceed 12 weeks in year one of the study. The interval between study injections can be extended to, but not more than, 16 weeks in year two of the study.

Enrolled subjects will have ETDRS BCVA, complete ophthalmic examination and SD-OCT evaluation using Spectralis machines at each visit. Fluorescein angiography will be done in the Monthly and TREX Cohorts at baseline (screening visit) and again at week 12, week 52, and week 104 or visits closest

to. Fluorescein angiography will be done in the GILA Cohort at baseline (screening visit), week 4, and every 90 days or greater (first visit that occurs \geq 90 days from previous fluorescein angiogram). See Appendix A for schedule of events from screening visit to week 104 and Appendix A.1 for the schedule of events between week 108 and week 156.

End-Point Visits

Subjects will continue to receive study treatments according to the above treatment protocol until week 155. A “Hard End-Point Visit” will occur at week 52, week 104, and week 156. A “Biologic End-Point Visit” will occur 4 weeks after the previous injection near the 12-month time point (week 46 – week 57), 24-month time point (week 92 – week 107). Only best corrected visual acuity and SD-OCT measurements will be recorded at these endpoint visits. No study treatment will be given at these end-point visits, unless the patient has a regular study treatment visit that occurs at these time points.

Fellow eyes not enrolled into a study group that have DME during the course of the study may be treated with standard of care macular laser photocoagulation and/or intravitreal injections of 0.3 mg of ranibizumab at the investigator’s discretion. Ranibizumab will be provided by Genentech for treatment of DME in the fellow eye.

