4.1.3 Exclusion Criteria

Subjects who meet any of the following criteria will be excluded from this study:

General Exclusion Criteria

- Pregnancy (positive urine pregnancy test) or lactation.
- Premenopausal women not using adequate contraception. The following are considered effective means of contraception: surgical sterilization or use of oral contraceptives, barrier contraception with either a condom or diaphragm in conjunction with spermicidal gel, an IUD, or contraceptive hormone implant or patch.
- Any other condition that the investigator believes would pose a significant hazard to the subject if the investigational therapy were initiated
- Participation in another simultaneous medical investigation or trial

Ocular Exclusion Criteria

Prior Ocular Treatment

- History of active proliferative diabetic retinopathy in the study eye on clinical exam
- History of vitrectomy surgery, submacular surgery, or other intraocular surgical intervention for diabetic macular edema in the study eye
- Any previous intravitreal drug delivery (e.g., intravitreal corticosteroid injection, anti-VEGF drugs including ranibizumab, or device implantation) in the study eye within 90 days of the screening visit.
- History of prior laser macular photocoagulation more than 90 days prior to screening will be eligible for study inclusion. However, if the investigator does not feel that additional laser photocoagulation can be safely performed or would benefit the patient, then the eye in consideration will be excluded.

- Evidence of vitreomacular interface abnormality or epiretinal membranes which may be responsible for macular edema

Concurrent Ocular Conditions

- Any concurrent intraocular condition in the study eye (e.g., cataract or macular degeneration) that, in the opinion of the investigator, could either:

Require medical or surgical intervention during the 24-month study period to prevent or treat visual loss that might result from that condition; or if allowed to progress untreated, could likely contribute to loss of at least 2 Snellen equivalent lines of BCVA over the 24-month study period.

- Active intraocular inflammation (grade trace or above) in the study eye
- Current vitreous hemorrhage in the study eye
- History of rhegmatogenous retinal detachment or macular hole (Stage 3 or 4) in the study eye
- Active infectious conjunctivitis, keratitis, scleritis, or endophthalmitis in either eye
- Aphakia in the study eye

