Subjects will continue to receive study treatments according to the above treatment protocol until week 104. A “Hard End-Point Visit” will occur at week 52, week 104, and week 156. A “Biologic End-Point Visit” will occur 4 weeks after the previous injection near the 12-month time point (week 46 – week 57), 24-month time point (week 92 – week 107), and 36-month time point (week 156). Only best corrected visual acuity and SD-OCT measurements will be recorded at these endpoint visits. No study treatment will be given at these end-point visits, unless the patient has a regular study treatment visit at these time points.

Study eyes which have not met criteria allowing them to extend to at least 6 weeks for two consecutive visits by the week 52 hard endpoint visit will receive a series of three intravitreal injections of ranibizumab 0.3 mg every 4 weeks regardless of OCT measurement, beginning at week 52 if treatment is indicated at that time or the first treatment visit thereafter. The study eye will resume treatment interval determinations based on the pre-specified criteria at the time of the third monthly intravitreal injection.

Fellow eyes not enrolled into a study group and that have DME during the course of the study may be treated with standard of care macular laser photocoagulation and/or intravitreal injections of 0.3 mg of ranibizumab at the Investigator’s discretion. Ranibizumab will be provided by Genetech for treatment of DME in the fellow eye.

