4.8 STATISTICAL METHODS

4.8.1 Analysis of the Conduct of the Study

The analysis of complete data (36-month treatment period) for the study will be performed when all patients have either completed the visit at month 36 or discontinued early from the study, all data collected from the study are in the database, and the database is locked.

Interim analysis of data from the 12-month period will be performed when all patients have either completed the visit at month 12 or discontinued early from the study. Treatment assignment will be unmasked to the personnel performing the analysis when all data collected through month 12 are in the database and the data have been cleaned and verified. The Peto group sequential procedure ($Z \pm 3.0$ at all interim analyses) will be used to control for the possibility of type I error arising from the 12 month interim analysis.

For the primary objective, power calculations for different margins were undertaken. Familywise alpha of 0.05 was divided equally among three TOST (two one sided test) procedures ($\alpha=0.0167$): (1) comparing TREX vs. GILA in the 60 patients enrolled with bilateral disease, (2) TREX vs. control (total $n=90$, controls $n=30$), and (3) GILA vs. control (total $n=90$, controls $n=30$). A standard deviation of 11 letters was used for the power calculations and based from the RISE/RIDE data for subjects with DME. The power calculations suggests that the minimum boundary of equivalence for TREX vs. GILA that we can demonstrate is ± 7 letters (less than two lines of vision) and ± 9 letters (less than two lines of vision) for TREX and GILA vs. controls. Paired sample t-test will be used to compare TREX vs. GILA and two sample t-test will be used to compare the two groups vs. controls.

Because of the potential for confounding of the effect when comparing the control group (monthly cohort) to the TREX and GILA groups, we will use linear regression modeling with change in ETDRS as outcome

and cohort as main effect controlling for potential confounders (e.g., age, race, sex).

Adverse events, number of injections, and number of office visits will be approached statistically with descriptive analyses with point estimates and confidence limits provided. Exploratory linear, logistic, and time-to-event models will be used to analyze the other secondary outcomes.

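### The exclusion for concurrent eye conditions looks ahead 24 months in a study that runs to 36, so it does not cover year 3

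*Combined protocol and SAP*

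**What the plan says.** Under Concurrent Ocular Conditions, section 4.1.3 of the combined protocol and SAP excludes a study eye with an intraocular condition, cataract and macular degeneration being the examples, if in the investigator's opinion either of two things could happen:

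- it could "Require medical or surgical intervention during the 24-month study period to prevent or treat visual loss" from that condition; or
- left untreated, it "could likely contribute to loss of at least 2 Snellen equivalent lines of BCVA over the 24-month study period".

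The rest of the plan mostly works to a longer horizon. Section 3.1 gives the Monthly cohort "Monthly intravitreal injections of 0.3 mg ranibizumab for 36 months", subject to as-needed treatment from week 104, and section 4.2 repeats the 36 months. Both sections place a hard end-point visit at week 156. Section 4.8.1 says: "The analysis of complete data (36-month treatment period) for the study will be performed" once all patients have reached month 36 or left the study. Sections 3.3.2 and 4.8.3 set secondary endpoints for line gain or loss, foveal thickness, retinopathy step change and progression at or through 36 months.

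The plan is not consistent on when study treatment ends. Section 3.1 says: "Subjects will continue to receive study treatments according to the above treatment protocol until week 155". The parallel sentence in section 4.2 says: "Subjects will continue to receive study treatments according to the above treatment protocol until week 104".

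The primary endpoint is at 24 months, with a window of weeks 92 to 107 (sections 2.1, 3.3.1 and 4.8.3).

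**The concern.** A prognostic exclusion of this kind keeps foreseeable vision loss from other eye disease out of the acuity endpoints. It can do so only over the period it covers. Here the period is called the study period but is one year shorter than the study period used for the final analysis and the late secondary endpoints.

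Year 3 is exposed in two ways. First, the proportions of eyes gaining or losing one or three lines are read at week 156, where loss from a cataract that was foreseeable at entry would count like any other loss. Second, from week 104 every arm moves to as-needed treatment, and one trigger is a loss of more than 5 letters since week 104 that is attributed to DME. In an open-label trial, a second progressive condition in the same eye makes that attribution harder. Section 4.5.1 adds a measurement complication: after week 104 a new refraction is done only at weeks 116, 128, 140 and 156. Surgery between those visits could leave acuity tested for a time with an outdated correction.

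Nothing in section 4.8 deals with intercurrent eye surgery. Section 4.8.4 analyses available cases without imputation, and no sensitivity analysis is described.

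**Working it through.** The plan gives no figure to reproduce. The check compares the stated horizons, converting weeks to months as weeks × 7 / 30.4375.

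**Horizons**

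- Exclusion, both limbs (4.1.3): 24 months. Week 104 × 7 / 30.4375 = 23.9 months.
- End of study treatment in 3.1: week 155 × 7 / 30.4375 = 35.7 months. In 4.2: week 104, or 23.9 months.
- Last hard end-point visit (3.1 and 4.2): week 156 × 7 / 30.4375 = 35.9 months.
- Final analysis (4.8.1): 36 months.
- Last secondary acuity and thickness time point (3.3.2 and 4.8.3): week 156.
- Primary window (3.3.1): weeks 92 to 107, or 21.2 to 24.6 months.

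**Follow-up outside the exclusion**

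- 156 − 104 = 52 weeks, and 52 / 156 = 33%.
- Four-weekly visits from week 108 to week 156: (156 − 108) / 4 + 1 = 13.

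**Primary endpoint**

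- The window runs at most 107 − 104 = 3 weeks past the look-ahead, so the primary endpoint is essentially inside it.

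**Scale of one event**

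- Assuming 5 letters per line, two lines are 2 × 5 = 10 letters. That exceeds the 5-letter loss named in the year-3 trigger, if the loss is attributed to DME.
- The line endpoints count change from Day 0, not from week 104. Section 1.3 cites a mean gain of 9 letters with ranibizumab at 1 year and similar findings at 2 years. An eye at that mean that then loses 10 letters ends at 9 − 10 = −1 letter from Day 0, which is not a one-line loss. An affected eye therefore need not change category.

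**Number of eyes affected**

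- The documents give no rate of cataract surgery, or of two-line loss from other eye disease, in year 3. The number of such eyes, and so the effect on any 36-month endpoint, cannot be computed.

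**The case against.** The strongest reply is that 24 months matches the primary endpoint, so the horizon may be deliberate. That is possible, and it is why the primary endpoint is safe. But the criterion refers to the study period, not the primary endpoint, and section 4.8.3 uses that same term for 36 months. The text gives no reason for the shorter horizon.

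Several stronger readings are tempting, and the documents do not support them.

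- A reader might infer that sites are obliged to accept these eyes. They are not: escaping one exclusion does not compel enrolment. The test rests on investigator opinion and the low threshold of what could happen. Section 4.1.2 requires clear media. Section 4.1.3 also excludes eyes whose images cannot be graded and, under systemic conditions, has a discretionary exclusion for findings that might affect interpretation, with no time limit. These may remove some such eyes, although none expressly looks ahead to year 3.
- A reader might infer that every other passage runs to 36 months. Section 4.2 still ends study treatment at week 104.
- A reader might infer a conflict with the inclusion criterion on compliance for the whole study. That criterion concerns the subject's compliance, this one the eye's prognosis, and a subject can satisfy both.
- A reader might infer that cataract loss directly triggers injections. The acuity trigger is limited to loss caused by DME, and the other trigger is an OCT thickness. What remains is possible misattribution.
- A reader might infer bias between arms or a definite shift in the 36-month percentages. The criterion applies identically before randomization, so by itself it creates no baseline imbalance, and any percentage would need an invented event rate.

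It also stands that the affected endpoints are secondary and that section 4.8.1 treats them descriptively or with exploratory models.

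**Conclusion.** The mismatch is real and stands in the current text. The criterion leaves the last 52 of 156 weeks uncovered: it does not exclude an eye whose cataract or other condition is expected to need intervention, or to cost two lines, only in months 25 to 36. The harm is added noise from causes other than DME in the 36-month secondary acuity endpoints and harder attribution of year-3 vision loss. The 24-month primary endpoint is essentially unaffected. The size cannot be computed from the documents; the letter arithmetic rests on an assumed 5 letters per line.

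The 24-month wording here and the week-104 sentence in section 4.2 look like remnants of a shorter design, but the documents do not confirm this. Nor do they say whether enrolment had closed before a third year was planned. Confidence is high for the mismatch only. It is still worth correcting, because this is an operative eligibility rule and the change is cheap.

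**What to change.** 1. Reconcile the look-ahead in both limbs of the criterion in section 4.1.3 with the 36-month study period. The cost is a two-place wording change and perhaps slightly more screen failures for early cataract. It helps only while enrolment is open.
2. In the same amendment, reconcile the statements in sections 3.1 and 4.2 on when study treatment ends. This point takes no position on which is right.
3. If eyes were already enrolled under the 24-month wording, report intraocular surgery after week 104 by arm. This takes one table.
4. Optionally, add a supplementary 36-month acuity analysis without those eyes, labelled as conditioning on a post-randomization event. Section 3.4 lists cataract development or progression as a potential safety issue of the drug or its route, and injection exposure differs between arms, so dropping operated eyes can introduce selection bias. It should not replace the analysis of all available eyes.

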4.2 METHOD OF TREATMENT ASSIGNMENT

All eyes which satisfy all inclusion/exclusion criteria will be randomized 1:2:2 into the Monthly:TREX:GILA Cohorts. Screening evaluations may be performed at any time within the 14 days preceding Day 0. Randomization will occur at Day 0.

Baseline Measurement For the TREX and GILA cohorts:

Eyes which have a central foveal thickness $\leq 325 \mu\text{m}$ at week 12, a "Primary Baseline" retinal thickness will be defined as the thinnest central foveal thickness on SD-OCT over the first four visits of monthly treatment. Eyes which have a central foveal thickness $> 325 \mu\text{m}$ at week 12 will continue to receive monthly intravitreal injections of 0.3 mg ranibizumab and guided laser photocoagulation every 3 months if leakage is present on fluorescein angiography until the central foveal thickness is $\leq 325 \mu\text{m}$, at which point their "Primary Baseline" retinal thickness will be established.

If at any point in the study period, the study eye has improved more than 20% from the primary baseline thickness for three consecutive visits and there is less than 50 microns of variability in central foveal thickness between these visits, then a "Secondary Baseline" retinal thickness will be established. This "Secondary Baseline" retinal thickness will then be used for treatment interval determinations from that point forward. If the study eye has improved more than 20% from the secondary baseline thickness for three consecutive visits and there

is less than 50 microns of variability in central foveal thickness between these visits, then a “Tertiary Baseline” retinal thickness will be established. This “Tertiary Baseline” retinal thickness will then be used for treatment interval determinations from that point forward.

Treatment Groups:

Monthly Cohort (30 eyes) – Study eyes will receive intravitreal injections of 0.3 mg ranibizumab every 28 days (+/- 7) for 36 months, relative to the date of the first injection (Day 0), unless indicated below.

Starting at week 104, study eyes will have the opportunity to undergo treatment on a pro re nata (PRN) basis. Thus, eyes who have a central subfield thickness (CST) \leq 325 microns at the week 104 visit, will not be given treatment at week 104. Eyes will continue to be seen every 4 weeks and will be given an intravitreal injection of ranibizumab 0.3 mg only if the CST is $>$ 325 microns. Eyes will also receive treatment if there is a $>$ 5 letter loss due to DME (compared to the vision at week 104), regardless of thickness on OCT.

Subjects will be evaluated for focal laser treatment at week 116, week 128, week 140, and week 152. If the subject has received \geq 2 intravitreal injections of ranibizumab within the prior 90 day period, then fluorescein angiography will be performed and focal laser treatment will be applied to any leaking microaneurysms. If the patient does not meet this criteria for focal laser treatment, then fluorescein angiography and focal laser treatment will be deferred and reassessed at the subsequent laser evaluation visit. Focal laser treatment and focal laser re-treatment will be administered no more than once every 90 days.

Focal laser therapy will be applied to all leaking microaneurysms on fluorescein angiography. Focal laser therapy will not be applied if significant macular ischemia is present involving the foveal avascular zone (once this has been determined additional fluorescein angiography and focal laser treatment planning should not be performed as the subject will no longer be eligible for focal laser treatment). Focal laser will also not be applied if treatment is considered too close to the foveal avascular zone or to macular edema not related to DME (cystoid macular edema, etc.). If no microaneurysms are present on fluorescein angiography, then focal laser therapy should be deferred and reassessed with repeat fluorescein angiography at the first visit that occurs after 90 days.

TREX Cohort (60 eyes) – Monthly intravitreal injections of 0.3 mg ranibizumab for four visits. At the fourth visit (Week 12), if the central foveal thickness is $\leq 325 \mu\text{m}$ then the eye will receive 0.3 mg ranibizumab and begin the extension phase of the study. For all subsequent visits in the extension phase, appropriate changes to the treatment interval with 0.3 mg ranibizumab (i.e. extend, maintain, reduce) will be made based on pre-specified SD-OCT criteria. Treatment is rendered at every visit, no earlier than 7 days before the target date and no later than 7 days after the target date, but the time between visits is individualized based on each subject's response to treatment. If the central foveal thickness is $> 325 \mu\text{m}$ at week 12, then the patient will continue to receive monthly intravitreal injections of 0.3 mg ranibizumab until the central foveal thickness is $\leq 325 \mu\text{m}$. Once the central foveal thickness is $\leq 325 \mu\text{m}$, then the study eye will begin the extension phase of the study.

Starting at week 104, study eyes will have the opportunity to undergo treatment on a pro re nata (PRN) basis. Thus, eyes who have a central subfield thickness (CST) ≤ 325 microns at the week 104 visit, will not be given treatment at week 104. Starting at week 104, eyes will be seen every 4 weeks and will be given an intravitreal injection of ranibizumab 0.3 mg only if the CST is > 325 microns. Eyes will also receive treatment if there is a > 5 letter loss due to DME (compared to the vision at week 104), regardless of thickness on OCT.

Subjects will be evaluated for focal laser treatment at week 116, week 128, week 140, and week 152. If the subject has received ≥ 2 intravitreal injections of ranibizumab within the prior 90 day period, then fluorescein angiography will be performed and focal laser treatment will be applied to any leaking microaneurysms. If the patient does not meet this criteria for focal laser treatment, then fluorescein angiography and focal laser treatment will be deferred and reassessed at the subsequent laser evaluation visit. Focal laser treatment and focal laser re-treatment will be administered no more than once every 90 days.

Focal laser therapy will be applied to all leaking microaneurysms on fluorescein angiography. Focal laser therapy will not be applied if significant macular ischemia is present involving the foveal avascular zone (once this has been determined additional fluorescein angiography and focal laser treatment planning should not be performed as the subject will no longer be eligible for focal laser treatment). Focal laser will also not be applied if treatment is considered too close to the foveal avascular zone or to macular edema not related to DME (cystoid

macular edema, etc.). If no microaneurysms are present on fluorescein angiography, then focal laser therapy should be deferred and reassessed with repeat fluorescein angiography at the first visit that occurs after 90 days.

GILA Cohort (60 eyes) – Monthly intravitreal injections of 0.3 mg ranibizumab for four visits combined with Guided LASer (GILA) photocoagulation to all microaneurysms in the area of DME at the second visit (Week 4). Fluorescein angiography is to be repeated approximately every 3 months (the first visit that occurs ≥ 90 days from the preceding fluorescein angiography visit). Guided laser will be repeated at those visits if leakage is present from microaneurysms. If the central foveal thickness is ≤ 325 μm at the fourth visit (Week 12), eyes will receive 0.3 mg ranibizumab and the extension phase will begin. For all subsequent visits in the extension phase, appropriate changes to the treatment interval with 0.3 mg ranibizumab (i.e. extend, maintain, reduce) will be made based on pre-specified SD-OCT criteria. Treatment is rendered at every visit, no earlier than 7 days before the target date and no later than 7 days after the target date, but the time between visits is individualized based on each subject's response to treatment. If the central foveal thickness is > 325 μm at week 12, then the patient will continue to receive monthly intravitreal injections of 0.3 mg ranibizumab and possible guided laser every 3 months until the central foveal thickness is ≤ 325 μm . Once the central foveal thickness is ≤ 325 μm , then the study eye will begin the extension phase of the study.

Starting at week 104, study eyes will have the opportunity to undergo treatment on a pro re nata (PRN) basis. Thus, eyes who have a central subfield thickness (CST) ≤ 325 microns at the week 104 visit, will not be given treatment at week 104. Starting at week 104, eyes will be seen every 4 weeks and will be given an intravitreal injection of ranibizumab 0.3 mg only if the CST is > 325 microns. Eyes will also receive treatment if there is a > 5 letter loss due to DME (compared to the vision at week 104), regardless of thickness on OCT.

After week 104, subjects will be evaluated for focal laser treatment in the same manner as the Monthly and TREX Cohorts. Subjects will be evaluated for focal laser treatment at week 116, week 128, week 140, and week 152. If the subject has received ≥ 2 intravitreal injections of ranibizumab within the prior 90 day period, then fluorescein angiography will be performed and focal laser treatment will be applied to any leaking microaneurysms. If the patient does not meet this criteria for focal laser treatment, then fluorescein angiography and focal laser treatment will be

deferred and reassessed at the subsequent laser evaluation visit. Focal laser treatment and focal laser re-treatment will be administered no more than once every 90 days.

Focal laser therapy will be applied to all leaking microaneurysms on fluorescein angiography. Focal laser therapy will not be applied if significant macular ischemia is present involving the foveal avascular zone (once this has been determined additional fluorescein angiography and focal laser treatment planning should not be performed as the subject will no longer be eligible for focal laser treatment). Focal laser will also not be applied if treatment is considered too close to the foveal avascular zone or to macular edema not related to DME (cystoid macular edema, etc.). If no microaneurysms are present on fluorescein angiography, then focal laser therapy should be deferred and reassessed with repeat fluorescein angiography at the first visit that occurs after 90 days.

- End-Point Visits

Subjects will continue to receive study treatments according to the above treatment protocol until week 104. A “Hard End-Point Visit” will occur at week 52, week 104, and week 156. A “Biologic End-Point Visit” will occur 4 weeks after the previous injection near the 12-month time point (week 46 – week 57), 24-month time point (week 92 – week 107), and 36-month time point (week 156). Only best corrected visual acuity and SD-OCT measurements will be recorded at these endpoint visits. No study treatment will be given at these end-point visits, unless the patient has a regular study treatment visit at these time points.

Study eyes which have not met criteria allowing them to extend to at least 6 weeks for two consecutive visits by the week 52 hard endpoint visit will receive a series of three intravitreal injections of ranibizumab 0.3 mg every 4 weeks regardless of OCT measurement, beginning at week 52 if treatment is indicated at that time or the first treatment visit thereafter. The study eye will resume treatment interval determinations based on the pre-specified criteria at the time of the third monthly intravitreal injection.

Fellow eyes not enrolled into a study group and that have DME during the course of the study may be treated with standard of care macular laser photocoagulation and/or intravitreal injections of 0.3 mg of ranibizumab at the Investigator’s discretion. Ranibizumab will be provided by Genetech for treatment of DME in the fellow eye.

